6.1.8 Conversion of Time Interval

In case a time interval was calculated in days and needs to be converted into weeks, months or years the following conversion factors need to be used:

1 week = 7 days

1 month = 30.4 days

1 year = 365.25 days

6.1.9 Pooling of Investigative Sites

Sites participating in this study are from Australia, Europe and North America. Due to the small numbers of subjects at each site, there is no plan to use site as a stratifying factor in the analyses; the primary analysis will use data pooled across site. The effectiveness and safety analyses may be presented by region.

6.1.10 Determination of Sample Size

The sample size justification as indicated in the study protocol is as follows: The sample size will be determined by the number of subjects in the three core studies (Study ZX008-1501, Study ZX008-1502, or Study ZX008-1504) who volunteer for the extension study and meet the necessary criteria for enrollment. Approximately 100-120 subjects are expected to participate in each of the core studies. Thus, if all of those participants also enrolled in the extension, the total sample size of the extension study would be between 300 and 360.

It is expected that this sample size will provide adequate exposure information for this orphan drug, to inform the label at time of marketing authorization, and would allow detection of at least one, two or three rare events with reasonable likelihood. As an example, if a slightly conservative estimate of the number of subjects enrolled in Study ZX008-1503 is set at n=270, the table below provides probability calculations for detecting at least one, 2, or 3 events, assuming various values for an underlying event rate of 1, 2, 3, 4, 5, or 10%:

Table 9: Probability calculations for specified adverse event occurrence rates

	Probability of detecting an adverse event in trial with n=270, with specified true event rate of:					
Probability of observing	10%	5%	4%	3%	2%	1%
≥1 event	100.0	100.0	99.998	99.97	99.6	93.4
≥2 events	100.0	99.999	99.98	99.7	97.2	75.3
≥3 events	100.0	99.989	99.88	98.8	90.7	50.7

6.2 SUBJECT CHARACTERISTICS

Individual subject data will be listed for all subjects in the SAF population. Unless otherwise specified, all data summaries will be overall and by Core study treatment group as described in Section 3.2 of this SAP.

6.2.1 Subject Disposition

Subject disposition will be presented for all subjects overall, and by treatment group in Core study for the Enrolled and SAF populations. Disposition information that will be summarized includes number of subjects who started treatment in the OLE study, number who withdrew prematurely, and reasons for withdrawal.

6.2.2 Protocol Deviations

Protocol deviations will be reviewed, and those deviations that are regarded as major will be summarized. Major protocol deviations affecting effectiveness or safety assessment may include:

- Non-compliance regarding intake of IMP
- Inappropriate intake of concomitant medication or background AEDs
- Other non-compliance

Multiple deviations can occur in the same subject and thus a subject can be counted in more than one deviation category.

All protocol deviations will be presented in a subject data listing for the SAF population sorted by subject within study site.

6.2.3 Background and Demographic Characteristics

Subject demographics and baseline characteristics will be summarized for the SAF and mITT.

6.2.3.1 Subject Demographics/Baseline Characteristics

The following demographic characteristics will be summarized for the data at entry into 1503:

- Age at Core Study entry [Years] / for de novo subjects, this will be the age at entry into 1503
- Age Category(<6 years or ≥6 years)
- Sex
- Race
- Ethnicity
- Height [m]
- Weight [kg]
- BMI [kg/m²]

All subject demographics data will be listed for the SAF populations.

6.2.3.2 Other Baseline Characteristics

Epilepsy/seizure history will be descriptively summarized as per data type (continuous or categorical).

All subject baseline characteristics will be listed for the SAF population.

6.2.4 Treatment Exposure and Compliance

6.2.4.1 Treatment Exposure

Treatment exposure data will be summarized for subjects' time on treatment in Study ZX008-1503 only and analyzed for the SAF population.

Duration of total exposure to fenfluramine hydrochloride (i.e., time on treatment (in days)) will be calculated per subject as the number of days with IMP intake during the trial, as follows:

$$\text{Duration of exposure} = \text{Date of last IMP intake} - \text{Date of first IMP intake} + 1$$

The number of days exposed to fenfluramine hydrochloride will be summarized overall and by treatment group using n, mean, standard error, median, minimum, Q₁, Q₃ and maximum.

The actual dose of medication consumed will be calculated and summarized overall and by treatment group using n, mean, standard error, median, minimum, Q₁, Q₃ and maximum.

The shift in dosage of ZX008 will be presented at each scheduled visit starting from Visit 3 – OLE Month 1 and going to Visit 16 – OLE Month 36 or End of Study. At the visit, the number of subjects who attended the visit will be provided with the dosage of ZX008 assigned to the subject at the last study drug dispense prior to the visit and the dosage of ZX008 assigned at the conclusion of the visit.

The duration of exposure to fenfluramine hydrochloride will be summarized in monthly periods based on the mean daily dosage in mg/kg/day and in mg/day. In addition, the duration of time in days based on the assigned dosage in mg/kg/day will be summarized. For the actual dosage summary, the periods where a subject has had a particular dosage assigned may not be concurrent.

6.2.4.2 Compliance to IMP Intake

Study medication is to be administered twice daily, and compliance is recorded in the eDiary as full (both doses), partial (less than full daily dose) or missed (both doses) each day. From this, compliance to IMP intake will be calculated by assuming that a missed dose=0% of dose consumed, partial=50% of dose consumed, and full=100% of dose consumed. For each subject, a daily compliance score will be thus obtained.

Compliance will be summarized for the SAF and mITT populations.

6.2.5 Prior and Concomitant Medications and/or Therapies (Non-medications)

Data are collected on the following CRFs:

- Prior AEDs (Prior AED)
- Concomitant AEDs (Con AED)
- Prior and concomitant medications (MEDS)
- Prior Non-medications (Prior Non-Meds)
- Concomitant non-medications (Con Non-Med)

Rescue medications are recorded in subjects' diary, however the CRF obtains a code list of a subject's planned rescue medications. This section does not discuss details of rescue medication use.

Medication (collected on the prior/concomitant medication eCRF page) will be coded using the World Health Organization Drug Dictionary (WHO-DD).

The following algorithm will be used to define prior/baseline and concomitant medications/therapies:

Medications/therapies can be prior/baseline only, concomitant only, or prior/baseline and concomitant, depending on the start and stop dates.

- Any medication/therapy whose start and stop dates were *before* the start of study medication in Study ZX008-1503 will be considered as a prior/baseline medication.
- Any medication initiated *after* commencement of study drug in Study ZX008-1503 will be regarded as being only concomitant.
- Medications that were initiated before study drug was started in Study ZX008-1503 and ended during or after the study will be considered as *prior/baseline and concomitant*.

The medication will be assumed to be prior/baseline medication if it cannot be definitively shown that the medication did not start or continue during the OLE treatment period.

If the start date or stop date of a medication/therapy is partially missing, the date will be compared as far as possible with the date of the start of administration of study drug. The following approach will be taken:

- If the start date of medication/therapy is complete and occurs on or after the day of the first dose in 1503, the medication will be assumed concomitant only. If the start date occurs prior to the first dose date but the end date is on or after the first dose date or the medication is recorded as ongoing, the medication will be considered concomitant.
- If the start day is missing but the start month and year are complete, a medication/therapy will only be excluded as being concomitant (i.e. regarded as prior only) if the start month/year is before the month/year of study drug administration and if the stop date (either full date, month and year if missing day, or year if missing month and day) is before study drug administration.
- If the start day and month are missing but the start year is complete, a medication/therapy will only be excluded as concomitant (i.e., will be regarded as prior/baseline only) if the start year is before the year of study drug administration and if the stop date (either full date, month and year if missing day, or year if missing month and day) is before study drug administration.
- If the start date is completely missing and the stop date is prior to first dose or completely missing, the medication/therapy will be assumed a prior/baseline medication only.

Prior/baseline and concomitant medications/therapies will be summarized and sorted alphabetically, separately, by Anatomical Therapeutic Chemical (ATC) categories (Level 2: pharmacological or therapeutic subgroup and Level 3: chemical or therapeutic or pharmacological subgroup) and WHO-DD drug code. For each medication/therapy, the number and percentage of subjects will be displayed.

Summary tables will be presented on the SAF population.

All prior/baseline and concomitant medications/therapies will be listed for the safety population.

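### SAP 6.2.5: the default for uncertain medication dates is worded against its own bullets, and a wholly undated record is classed as prior only

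*SAP*

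**What the plan says.** SAP 6.2.5 sets up three classes: "Medications/therapies can be prior/baseline only, concomitant only, or prior/baseline and concomitant, depending on the start and stop dates". It then gives a general rule for doubtful cases: "The medication will be assumed to be prior/baseline medication if it cannot be definitively shown", the thing to be shown being that the drug was neither begun nor carried on in the open-label period.

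The bullets that follow are more specific:

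- **Complete start before first dose.** If the stop is on or after first dose, "or the medication is recorded as ongoing, the medication will be considered concomitant".
- **Start day missing.** "a medication/therapy will only be excluded as being concomitant (i.e. regarded as prior only) if the start month/year is before" that of first dose, and the stop also precedes study drug.
- **Start day and month missing.** "a medication/therapy will only be excluded as concomitant (i.e., will be regarded as prior/baseline only) if the start year is before" that of first dose, and the stop again precedes study drug.
- **Start completely missing.** "If the start date is completely missing and the stop date is prior to first dose or completely missing", the drug is taken as prior/baseline use alone.

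Section 6.2.6 defines prior and concomitant antiepileptic treatments in a similar way. The footnote to Table 14.1.4.4.1 (concomitant antiepileptic treatment) refers missing or partial AED dates back to 6.2.5.

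**The concern.** When it is unclear whether a drug was taken on study, the cautious course is to count it as concomitant unless the dates rule that out. The default sentence does the reverse, and so contradicts the two partial-start bullets below it. A programmer has no stated order of precedence between them.

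The last bullet does not depend on how the default sentence is read. It treats a wholly unknown stop in the same way as a stop known to precede first dose.

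The SAP also takes the opposite line for adverse events. In 6.1.7.2 an event that might have begun after first IMP is treated as treatment-emergent, and Table 8 assumes that an event with no ongoing flag and no end date is still present. No reason is given for a different direction with medications.

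Three sets of outputs depend on the concomitant flag:

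- Table 14.1.4.4.1 counts subjects by concomitant AED.
- Table 14.1.4.4.2 gives the number of concomitant AEDs in rows 1 to 6 with no zero row, so a subject whose AEDs were all left unflagged would have no row. Yet 6.3.1.6 says that at least one background AED had to remain.
- Tables 14.4.1.6 and 14.4.1.8 split weight loss and gain by concomitant topiramate. An unflagged user would be counted among the non-users.

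**Working it through.** The SAP states no figure on this point. The check is an enumeration of the rules in 6.2.5.

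**Inputs**

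- Six start-date states: complete and before first dose; month and year known and before; month and year the same as first dose; only the year known and before; only the year known and the same; completely missing.
- Seven stop-date states: complete and before first dose; partial and before; partial and spanning first dose by month; partial and spanning it by year; after first dose; completely missing; flagged ongoing.

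This gives 6 × 7 = 42 combinations. On-study use is excluded when the stop is known to precede first dose (two stop states) and possible in the other five, so it is possible in 6 × 5 = 30.

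**Class given by the bullets in those 30 combinations**

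| Start date | Possible | Concomitant | Prior only | Ambiguous | No bullet |
|---|---|---|---|---|---|
| Complete, before first dose | 5 | 2 | 0 | 0 | 3 |
| Month and year before | 5 | 5 | 0 | 0 | 0 |
| Same month and year | 5 | 5 | 0 | 0 | 0 |
| Year before | 5 | 5 | 0 | 0 | 0 |
| Same year | 5 | 5 | 0 | 0 | 0 |
| Completely missing | 5 | 0 | 1 | 1 | 3 |
| Total | 30 | 22 | 1 | 1 | 6 |

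**Reading the table**

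1. In 22 combinations the bullets say concomitant while the default sentence points to prior/baseline. This is the contradiction.
2. The one explicit prior-only result is start and stop both completely missing. If the start year alone were known, the stop still being blank, the preceding bullet would make the same drug concomitant. Losing the year reverses the class.
3. The ambiguous case is a missing start flagged ongoing. The ongoing rule sits in the bullet for complete start dates, and a blank stop could be read as completely missing under the last bullet.
4. Six combinations have no bullet and fall to the default sentence. Three have a complete pre-dose start with a stop that is missing, or partial and spanning first dose by month or by year, and no ongoing flag. Three have a missing start with a stop that spans first dose (by month or by year) or follows it.
5. The exposed set is therefore 30 − 22 = 8 combinations. For AEDs one of these is settled elsewhere: the footnote to Table 14.1.4.4.1 counts a stop date after first dose as concomitant, which covers a missing start with a later stop. That leaves 8 − 1 = 7.

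In the three combinations with a complete pre-dose start, it is already known that the drug is prior. The open question is whether it is also concomitant, and the default sentence never grants that status.

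**The case against.** The strongest reply is that the default sentence is a drafting slip with little reach. It says prior/baseline without the word only, and one of the three classes is prior and concomitant together. The specific bullets would normally take precedence, and they handle most uncertain dates conservatively. An AED that continues on study can be entered as ongoing in the stop-date column of the AED listing. AEDs have separate Prior AED and Con AED CRF pages, all records are listed, and the affected tables are descriptive. The models in 6.3.1.3 and 6.3.1.4 contain no concomitant-AED term.

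Most of this stands, and it limits the point. It does not remove the last bullet, which does say only, or the six combinations that no bullet covers. Section 6.2.5 classifies by dates and not by CRF page, so the separate pages do not correct the flag.

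Several stronger inferences are tempting but not supported:

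- **That the default sentence itself makes drugs prior only and generally hides concomitant AEDs.** The sentence lacks that word, and 22 of the 30 combinations are already concomitant under the bullets.
- **That every record with both dates blank is misclassified.** A drug that did stop before the OLE is correctly prior.
- **That long-standing AEDs are the records most likely to lack dates.** The SAP says nothing on this.
- **That a given share of undated records understates each AED by the same share.** The AED table counts a subject once per preferred name, so another dated record of the same drug keeps the subject counted.
- **That the AED-change table (14.2.1.6) is distorted.** Its programming note says that a change has still to be defined, and a record without dates could not be placed in a month under either default.

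**Conclusion.** The point holds in a limited form. The default sentence in 6.2.5 is worded backwards and conflicts with the partial-start bullets. The last bullet makes a wholly undated record prior only although the drug may have continued on study, and a missing start flagged ongoing has no clear class.

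The exposure is confined to wholly missing start dates, and to complete pre-dose starts whose stop is missing or partial and spans first dose, with no ongoing flag. Within that set the error goes one way: a possibly concomitant drug can be left out of the concomitant-AED summaries, or a possible topiramate user placed in the subset without it. How many records or subjects are affected cannot be determined from the SAP; the counts above describe rules and say nothing about frequency. The conclusion assumes that the bullets override the default wherever they apply. If a programmer gave the default sentence precedence, more records would be affected.

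This is a wrong stated rule that should be corrected before the final analysis. It affects descriptive summaries and does not bear on the modelled seizure endpoints.

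**What to change.** Amend 6.2.5 in three places:

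1. Reword the default: a drug is concomitant, and also prior if it could have started earlier, unless the available date parts show that it stopped before the first OLE dose.
2. Restrict the last bullet's prior-only result to stop dates known to precede first dose. Treat a completely missing or ongoing stop as concomitant. For wholly undated AED records, the source CRF page (Prior AED or Con AED) may be used to settle the class.
3. State that the corrected default governs any combination that no bullet covers. The two partial-start bullets can stay as they are.

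The cost is a few sentences and a small change to the derivation of the concomitant flag. The downside is that a few undated drugs that had truly stopped may be counted as concomitant; using the CRF page limits this for AEDs.

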6.2.6 Prior and Concomitant Antiepileptic Treatment

Treatments (collected on the prior/concomitant antiepileptic treatment eCRF page) will be coded using the World Health Organization Drug Dictionary (WHO-DD).

Prior and concomitant antiepileptic treatments will be defined and analyzed for the SAF population similar to concomitant medications as described in section 6.2.5.

All prior and concomitant antiepileptic treatments will be listed for the SAF population.

6.2.7 Medical History

All ongoing conditions and relevant medical history from the past 5 years (including all major hospitalizations and surgeries) as well as the subject's current medical status and current medications will be carried over from the core study. AEs starting during the core study will be counted as medical history if they conclude prior to start of 1503. Ongoing AEs will be included as such in 1503.

Medical history will be summarized and sorted alphabetically, by primary System Organ Class and Preferred Term coded via the most recent version of Medical Dictionary for Regulatory Activities (MedDRA). The number and percentage of subjects will be displayed for each System Organ Class and Preferred Term within treatment group.

Medical history will be presented for the SAF population.

6.3 EFFECTIVENESS ANALYSES

All effectiveness and exploratory data will be summarized overall and by treatment group in Core study as described in Section 3.2 of this SAP. Continuous data will be summarized using descriptive statistics including means, standard deviations, medians, lower and upper quartiles, and ranges. Categorical variables will be summarized with frequencies and percentages. Point estimates and 95% confidence intervals will be calculated for key parameters as warranted. No formal comparison of treatment groups is planned.

Analyses of the key effectiveness endpoints will be performed on the mITT population, except where noted.

6.3.1 Convulsive Seizure Frequency

The key effectiveness endpoint is the change in the convulsive seizure frequency per 28 days between the pre-ZX008 Baseline and OLE Treatment Period. To aid in assessing the effect of OL treatment after treatment with blinded fixed doses, CSF per 28 days will also be presented for each pre-OLE cohort for the last weekly measure in double-blind treatment (T+M) for the entire OLE treatment period, and separately for the first, second and third months of the OLE. In addition, CSF over the remainder of the OLE treatment period will be presented, for 3-month intervals. The next section defines variables associated with these endpoints.

6.3.1.1 Variables (Estimands)

Two key CSF-related variables will be defined:

- (1) the difference in convulsive seizure frequency per 28 days (CSF) for the open-label Treatment Period (Day1 to EOS) compared to the Baseline (Core Study);
- (2) the difference in CSF for the Month2 to EOS (Day 31 to EOS) time point compared to the Baseline (Core).

Additional variables associated with the assessment of CSF are:

- Baseline (Core), Core Study (T+M), Core Study Final Week [Note: The Core Study Final Week is a subset of the Core Study (T+M) period.]

- CSF during the following time intervals: Month 1, Month 2, Month 3, Month 4-6, Month 7-9, Month 10-12, Month 13-15, Month 15-18, Month 19-21, Month 22-24, Month 25-27, Month 28-30, Month 31-33 and Month 34-36.

The frequency of convulsive seizures during a given interval will be derived from the number and type of events recorded in subject diaries. For each subject, the seizure frequency per 28 days will be calculated as the number of seizures recorded during the period, divided by the number of days in the period and multiplied by 28. The convulsive seizure frequency will be calculated from all available data collected during the relevant interval.

The Baseline (Core) convulsive seizure frequency, or CSF_{BC} , is calculated as in the Core Study using the CSF from the 42 days immediately preceding the Randomization visit in the Core Study. For any individual subject, the convulsive seizure frequency per 28 days during the baseline period (CSF_{BC}) will be derived as follows:

$$CSF_{BC} = \frac{28 \times \text{Total number of convulsive seizures during the core study baseline period}}{\text{Total number of days in the core study baseline period with nonmissing diary data}}$$

For each treatment group, the mean is obtained by averaging over the subjects in the treatment group.

The convulsive seizure frequency per 28 days for the Core Study T+M period (CSF_{CTM}) is defined below:

$$CSF_{CTM} = \frac{28 \times \text{Total number of convulsive seizures during the core study T + M period}}{\text{Total number of days in the core study T + M period with nonmissing diary data}}$$

The convulsive seizure frequency per 28 days for the Core Study Final Week of T+M (CSF_{CSFW}) is defined below:

$$CSF_{CSFW} = \frac{28 \times \text{Total number of convulsive seizures during the core study final week}}{\text{Total number of days with nonmissing diary data during the core study final week}}$$

Additionally for the other intervals (Month 1 through Month 36) defined in Table 7a, the convulsive seizure frequency per 28 days for that interval, $CSF_{OLE,i}$, $i=1, 2, 3, \dots, 14$, is defined as follows:

$$CSF_{OLE,i} = \frac{28 \times \text{Total number of convulsive seizures in the } i\text{th interval}}{\text{Total number of days in the } i\text{th interval with nonmissing diary data}}$$

The two key effectiveness measures, CSF_{E1} and CSF_{E2} , will be calculated as follows:

$$CSF_{E1} = \frac{28 \times \text{Total number of convulsive seizures from Day 1 to EOS}}{\text{Total number of days from Day 1 to EOS with nonmissing diary data}}$$

$$CSF_{E2} = \frac{28 \times \text{Total number of convulsive seizures from Day 31 to EOS}}{\text{Total number of days from Day 31 to EOS with nonmissing diary data}}$$

For each analysis group, the mean is obtained by averaging over the subjects in the analysis group.

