5.3 MODIFIED INTENT-TO-TREAT (MITT) POPULATION

The mITT Population is defined as all enrolled subjects who receive at least one dose of ZX008 and have at least one month (30 days) of valid seizure data during the open label extension. Effectiveness analyses, such as evaluating the change in the frequency of convulsive seizures, will be performed on the mITT Population.

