Pre-OLE	N/A	-1	Core Study Final * Week	End of T+M in Core Study – 6 days, to End of T+M in Core Study
Pre-OLE de novo	N/A	-99	Baseline (OLE)*	Day -28 to Day -1 of Study ZX008-1503
OLE	3	1	Month 1 (OLE)	1-30
OLE	4	2	Month 2 (OLE)	31-60
OLE	5	3	Month 3 (OLE)	61-90
OLE	6	4	Month 4-6 (OLE)	91-180
OLE	7	5	Month 7-9 (OLE)	181-270
OLE	8	6	Month 10-12 (OLE)	271-360
OLE	9	7	Month 13-15 (OLE)	361-450
OLE	10	8	Month 16-18 (OLE)	451-540
OLE	11	9	Month 19-21 (OLE)	541-630
OLE	12	10	Month 22-24 (OLE)	631-730
OLE	13	11	Month 25-27 (OLE)	731-820
OLE	14	12	Month 28-30 (OLE)	821-910
OLE	15	13	Month 31-33 (OLE)	911-1000
OLE	16	14	Month 34-36 (OLE)	1001-1095
OLE	NA	99	Month 01-EOS (ENDPT1)	1 to min(Last Dose date, Visit 16 date)
OLE	NA	98	Month 02-EOS (ENDPT2)	31 to min(Last Dose date, Visit 16 date)

Note: EOS/ET date = Visit 16 date. Per protocol, Visit 17 is end of the OLE Phase.

T+M=Titration + Maintenance in Core Study.

*Subjects in Study ZX008-1504 Cohort 1 will not have a baseline(core), For those subjects, the Core Study(T+M) represents all their seizure data during the transition period in the core study. Their core study final week will be the last 7 days of seizure data prior to the first visit in ZX008-1503. De novo subjects start Study ZX008-1503 treatment after a screening period.

**Analysis visit numbers are not the same as nominal visit numbers.

Table 7b. Time Intervals for Questionnaires*

Analysis Phase/Period	Scheduled Visit Number in ZX008-1503	Analysis Visit Number*	Time Interval (label on output)	Time Interval (Day)	Target Time Point (Day)
Pre-OLE	N/A	-99	Baseline (Core)	<1	Core Study Day -42 to Day-1 of Core Study
Pre-OLE	1	1	Baseline (OLE)	1	1
OLE	3	3	Month 1 (OLE)	21 to 44	30
OLE	4	4	Month 2 (OLE)	45 to 74	60
OLE	5	5	Month 3 (OLE)	75 to 134	90
OLE	6	6	Month 6 (OLE)	135 to 224	180
OLE	7	7	Month 9 (OLE)	225 to 314	270
OLE	8	8	Month 12 (OLE)	315 to 409	365
OLE	9	9	Month 15 (OLE)	410 to 499	455
OLE	10	10	Month 18 (OLE)	500 to 589	545
OLE	11	11	Month 21 (OLE)	590 to 679	635
OLE	12	12	Month 24 (OLE)	680 to 774	730
OLE	13	13	Month 27 (OLE)	775 to 864	820
OLE	14	14	Month 30 (OLE)	865 to 954	910
OLE	15	15	Month 33 (OLE)	955 to 1044	1000
OLE	16	16	Month 36 (OLE)	1045 to 1109	1095
OLE	OLE Last Visit**	99	Last Value	Day 2 to Visit 17 date	

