6.1.7 Handling of Dropouts and Missing Data

6.1.7.1 Missing Data

There will be no explicit imputation of missing data for effectiveness endpoints.

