Subjects discontinued trial early:	xx (xxx.x%)	xx (xxx.x%)	xx (xxx.x%)
Reasons for early trial discontinuation:			
Reason 1	xx (xxx.x%)	xx (xxx.x%)	xx (xxx.x%)
Reason 2	xx (xxx.x%)	xx (xxx.x%)	xx (xxx.x%)
---	xx (xxx.x%)	xx (xxx.x%)	xx (xxx.x%)
---	xx (xxx.x%)	xx (xxx.x%)	xx (xxx.x%)
Completed study	xx (xxx.x%)	xx (xxx.x%)	xx (xxx.x%)

Programming Notes:

- Information on this table comes from CRF 6, 14, 33 and 34.

Treatment Group for Part 2 of 2:
Groups 1, 6 and 7

Programming Notes: Use the shell for 14.1.1.1 for

Table 14.1.1.1.1
Subject disposition
All Enrolled Subject (Japan).

Table 14.1.1.2
Major protocol deviations
Safety Population

	Gp1 (N = XX) [1]	Gp8 (N = XX) [2]	ZX008 OL (N = XX)	De Novo Subjects (N = XX)
No. (%) Subjects with at Least One MPD	xx (xxx.x%)	xx (xxx.x%)	xx (xxx.x%)	xx (xxx.x%)
Type of MPD				
MPD 1	xx (xxx.x%)	xx (xxx.x%)	xx (xxx.x%)	xx (xxx.x%)
MPD 2	xx (xxx.x%)	xx (xxx.x%)	xx (xxx.x%)	xx (xxx.x%)
MPD 3	xx (xxx.x%)	xx (xxx.x%)	xx (xxx.x%)	xx (xxx.x%)

MPD = Major protocol deviation

Note: Subjects may have had more than one MPD.

Programming Note: Use the shell for 14.1.1.2 for

Table 14.1.1.2.1
Major protocol deviations
Safety Population (Japan)

**Table 14.1.1.3
Study Populations**

	Gp1 (N=xx)	Gp2 (N=xx)	Gp3 (N=xx)	Gp4 (N=xx)	Gp5 (N=xx)	Gp9 (N=XXX)	De Novo Subjects (N=xxx)
Enrolled (ITT) Population[1]	XX	XX	XX	XX	XX	XX	XX
Modified ITT (mITT) Population[2]	XX	XX	XX	XX	XX	XX	XX
Safety (SAF) Population [3]	XX	XX	XX	XX	XX	XX	XX

Notes:

[1] Enrolled (ITT) population: All subjects who gave informed consent or assent for entry into Study ZX008-1503.

[2] Modified ITT Population: All enrolled subjects who receive at least one dose of ZX008 and for whom at least 30 days of diary data are available. [All subjects on study from Day 30 of OLE period onward are included in the mITT population.]

[3] Safety population: All subjects who received at least one dose of ZX008 during the open label extension.

Programming note: For [2] include any subject who has any data from Study Day 30 onward.

Programming note: Use the shell for 14.1.1.3 for

Table 14.1.1.3.1
Study Populations (Japan)

Table 14.1.2.1
 Demographic and Baseline Characteristics
 Safety Population

	Gp1 (N=xx)	Gp2 (N=xx)	Gp3 (N=xx)	Gp4 (N=xx)	Gp5 (N=xx)	ZX008 OL (N=XXX)	De Novo Subjects (N=xxx)
Age (years)							
N	XX	XX	XX	XX	XX	XX	XX
Mean	XX.X	XX.X	XX.X	XX.X	XX.X	XX.X	XX.X
SD	XX.XX	XX.XX	XX.XX	XX.XX	XX.XX	XX.XX	XX.XX
Median	XX.X	XX.X	XX.X	XX.X	XX.X	XX.X	XX.X

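### Interval and Month 2 to EOS seizure frequencies have no minimum number of diary days, so a short seizure-free partial window counts as a 100% response

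*SAP*

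**What the plan says.** Section 6.3.1.1 sets the rule for every seizure-frequency variable: "The convulsive seizure frequency will be calculated from all available data collected during the relevant interval". The denominator of CSF_E2, one of the two key measures, is "Total number of days from Day 31 to EOS with nonmissing diary data", and the interval formula has the same form. The running text of the same section gives another denominator, with the count "divided by the number of days in the period and multiplied by 28". Neither sets a minimum. Table 7a starts the CSF_E2 window on Day 31 and ends it at the earlier of the last dose and Visit 16. Its quarterly windows start at Day 91.

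Section 6.1.7.1 adds only this: "There will be no explicit imputation of missing data for effectiveness endpoints". The one completeness rule is mITT entry in 5.3, under which subjects must "have at least one month (30 days) of valid seizure data during the open label extension". The programming note to the Table 14.1.1.3 shell is looser and tells programmers to "include any subject who has any data from Study Day 30 onward".

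Section 6.3.2.3 plans responder proportions at 25%, 50%, 75% and 100% for the OLE period, its monthly periods and Month 2 to EOS. The Table 14.2.2.1 shell repeats them for the later windows up to Month 36. Section 6.3.1.2 tests each change over time. Tables 14.2.1.1.1 and 14.2.2.1 are marked for the 2018 interim and the 120-day update, and their Japan versions for the Japan report.

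**The concern.** The 30 valid days required for mITT may lie anywhere in the OLE. They can all fall before Day 31, and they do not bear on any single later window. A subject's last window may then hold only a few days. Scaled to 28 days, such a window tends to give either 0, which is a 100% reduction whatever the baseline, or a value far above the subject's usual rate: one seizure in one diary day gives a frequency of 28.

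Readers will take a 100% reduction as seizure freedom over the labelled interval. If two or three diary days can produce it, the 75% and 100% proportions by interval partly measure window length. Interim reports are the most exposed, because most ongoing subjects are part-way through a window at the cut.

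**Working it through.** The SAP gives no figure on this point: no minimum days, no expected share of partial windows, and no baseline rate except the de novo entry minimum of 4 convulsive seizures per 4 weeks (Table 4, footnote b). Nothing of the plan's own can be reproduced, so the size below rests on assumed rates shown as a range.

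**1. The formulas on short windows.** CSF = 28 × seizures / diary days, and percentage change = (CSF − baseline) × 100 / baseline.
- Valid diary on Days 1 to 33: the subject is in mITT and CSF_E2 rests on 33 − 30 = 3 days. With no seizures on them, CSF_E2 = 0 and the change is −100%, whatever happened on Days 1 to 30.
- Leaving or cut off on Day 95: the Month 4-6 value rests on 95 − 90 = 5 of 90 days.
- Both denominators in 6.3.1.1 give 0 when no seizure is recorded, so their disagreement does not help.

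**2. Chance of a false 100% response under a simple Poisson model with an unchanged rate:** exp(−rate × days / 28).

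| Rate per 28 days | 3 days | 7 days | 15 days | 28 days |
|---|---|---|---|---|
| 4 | 65% | 37% | 12% | 1.8% |
| 8 | 42% | 14% | 1.4% | 0.03% |
| 12 | 28% | 5% | 0.2% | about 0 |
| 20 | 12% | 0.7% | about 0 | about 0 |

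**3. With over-dispersion.** Simulation, no effect: subject rate gamma (shape 4), a gamma multiplier per period (shape 4), Poisson counts, a 42-day baseline with at least 6 seizures, and 200,000 subjects per setting. Independent re-runs agree to within about 0.2 points. False 100% responders by window length:

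| Mean per 28 days | Full 90 days | 1 to 90 days | 1 to 14 days | 1 to 7 days |
|---|---|---|---|---|
| 6 | 0.1% | 6.5% | 31.9% | 47.3% |
| 12 | 0.0% | 3.5% | 19.6% | 32.0% |
| 20 | 0.0% | 2.0% | 12.3% | 21.4% |

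False responders at 75% or more, at mean 12, rise from 5.5% (full window) to 9.5% (1 to 90 days).

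**4. From window to table.** These percentages apply only to subjects with a partial window. If 10% of windows are partial at mean 12, the reported 100% rate rises by 0.10 × 3.5% = 0.35 points. If those 10% were all 1 to 7 days long, the rise would be 0.10 × 32.0% = 3.2 points.

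**5. What each cut leaves for CSF_E2** (sections 1 and 6.7, if dosed on entry).
- 2018 interim: entry by 13 March with diary to 18 June reaches at least Day 98, so 68 days after Day 30. The latest entrants have a Month 4-6 value from 98 − 90 = 8 days.
- 120-day update: entry by 31 December 2018 with data to 15 February 2019 reaches at least Day 47, so about 17 days after Day 30.
- Japan: all subjects have reached Month 3, so about 60 days after Day 30.

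**6. Early dropout and CSF_E2.** Assume constant dropout of 10 to 20% per year and the 320 subjects from the double-blind studies in Table 1. Then 320 × 0.10 × 7/365 = 0.6 to 320 × 0.20 × 7/365 = 1.2 subjects leave on Days 31 to 37. At 32%, that is about 0.2 to 0.4 false 100% responders.

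**The case against.** Using all available data is a defensible choice, and the stakes are limited. The primary objective is safety, 6.1.1 cautions against over-reading within-group changes, and the null hypothesis written in 6.3.1.2 concerns CSF_E1. Log transformation, the rank ANCOVA and the signed-rank test also damp very high values. All of that stands, but it does not answer the responder tables, where a zero from three days is a full response.

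Three stronger readings are tempting, and the document does not support them.
- A reader might infer that interim cuts also distort the MMRM. No interim runs it: 6.3.1.3 and 6.3.1.4 keep the ANCOVA and MMRM out of the Japan interim, and Tables 14.2.1.2 to 14.2.1.5 are marked for no interim report. The MMRM is exposed only at the final analysis.
- A reader might infer that CSF_E2 is unreliable at every cut. Step 5 shows that ongoing subjects have roughly 16 days or more after Day 30. A very short CSF_E2 needs dropout soon after Day 30 or a very sparse diary, and step 6 suggests that few subjects are affected.
- A reader might take the percentages in step 3 as inflation of the reported tables. They are conditional on a partial window, and a subject who stops on a window boundary has none.

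A strict cut-off also has a cost. Dropouts include subjects leaving for lack of efficacy, a listed reason in Listing 16.2.1.1, and removing their last windows could tilt the results favourably.

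**Conclusion.** The point holds for the by-interval responder tables, the by-interval summaries and the signed-rank tests, and in a minor way for CSF_E2. As written, the rule turns a few seizure-free diary days into a 100% response for the whole labelled interval. Conditional on a partial window, the false rate is about 2 to 6.5% (1 to 90 days) or 21 to 47% (1 to 7 days). The effect on a table scales with the share of partial windows, which the SAP does not give, and is largest at interim cuts. These sizes rest on assumed means of 6 to 20 per 28 days and on the assumed dispersion. CSF_E1 is protected as 5.3 is worded, but the looser programming note to Table 14.1.1.3 would weaken that protection. The gap should be closed, but it does not undermine the main effectiveness result.

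**What to change.** In 6.3.1.1 and 6.3.2.3, compute interval responder status and the by-interval CSF summaries and tests only when the window holds a prespecified minimum of non-missing diary days, for example 15 for monthly and 28 for quarterly windows. Compute CSF_E2 only with at least 28 diary days after Day 30. On the Poisson figures, 28 days holds the false 100% rate to 1.8% at a rate of 4 and about zero from 8 upward. Fifteen days still leaves 12% at a rate of 4, so the sponsor should set the monthly value against the baseline rates it already holds.

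Report the number of windows excluded and those subjects' reasons for leaving. Keep the all-available-data version as a sensitivity analysis. Leave the MMRM on all data, with the restricted version as its sensitivity analysis. Align the Table 14.1.1.3 programming note with the 30-valid-day rule in 5.3.

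The cost is a few sentences, a data flag and one repeated set of tables. Some partial windows, including those of subjects leaving for lack of efficacy, drop out of the main by-interval tables. The sensitivity analysis covers them, and their days still count in CSF_E1.
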